17.0 COVID-19 RELATED ANALYSIS

To eliminate immediate potential hazards to patients and study staff due to the COVID-19 pandemic while ensuring patients safety and maintaining data integrity, the protocol amendment #2 has been sent to sites to allow remote visits.

This section specifies analyses for evaluating the impact of COVID-19.

17.1 EFFICACY EVALUATION

Due to the nature of the patient CDRS-R assessment, the interview may be performed remotely provided that the patient has access to a videoconferencing platform where the rating clinician can visually see the patient during the discussion. Minimal disruption is expected for this endpoint.

17.2 SAFETY AND OTHER EVALUATION

This section specifies analyses related to the COVID-19 pandemic from the following aspects:

- Disposition
- Study visit (missing entire visit due to COVID-19 or missing assessments due to COVID-19)
- Protocol deviation
- Study drug disruption due to COVID-19
- TEAEs related to COVID-19

The Safety Population will be used for the planned analyses described above.

The number of patients impacted by COVID-19 during the study will be summarized by treatment group and overall. In addition, the number of patients impacted by COVID-19 and their corresponding disposition status in the double-blind treatment period, downtaper period, and follow-up period will be summarized, respectively.

The number of patients who missed at least one entire visit due to COVID-19 will be summarized by treatment group and overall. Furthermore, the number of patients who missed at least one assessment due to COVID-19 will be summarized by assessment category (laboratory, C-SSRS, vital signs, and ECG) and overall. Similar summarized will by provided by visit.

The protocol deviations that occur due to COVID-19 will be summarized and listed separately.

The number of patients with study drug disruption due to COVID-19 will be provided as well. The number of patients with TEAEs related to corona virus infection or coronavirus test positive will be provided. Supporting listings for the described analyses above will be provided.

18.0 CHANGES TO ANALYSES SPECIFIED IN PROTOCOL

None.

20.0 APPENDICES

APPENDIX I. PATTERN-MIXTURE MODEL DETAILS

For repeated measures with the monotone missing mechanism, the pattern-mixture model with non-future dependent missing assumption, proposed by Kenward et at. (2003), provides a feasible solution to accommodate certain missing not at random (MNAR) mechanism. The methodology relies on constructing unidentifiable conditional densities using identifiable densities and borrows techniques from standard multiple imputation.

1. Non-Future Dependent Missing Assumption

Assume there are T designed visits in a longitudinal study and let y_i (i = 1,2,...,T) represent patient's measurement at Visit i. When the missing mechanism is monotone, the pattern of missing data can be defined by the number of measurements (L) actually observed from the patient. Let $f(y_i,...,y_j \mid L=t)$ denote the conditional density of $y_i,...$ y_j , given that the last observed measurement is at Visit t. Then the overall density function for Pattern t can be written as

$$f(y_{1},...,y_{T} | L = t) = f(y_{1},...,y_{t} | L = t) f(y_{t+1} | y_{1},...,y_{t}, L = t)$$

$$\times \prod_{s=t+2}^{T} f(y_{s} | y_{1},...,y_{s-1}, L = t)$$
(1)

Note on the right hand side of (1) the first factor is clearly identifiable from the observed data, while the second and the beyond are not, due to lack of available data. The second factor $f(y_{t+1} \mid y_1,...,y_t, L=t)$ could be identifiable based on an assumed relationship between $f(y_{t+1} \mid y_1,...,y_t, L=t)$ and $f(y_{t+1} \mid y_1,...,y_t, L \ge t+1)$. The third and beyond factors $f(y_s \mid y_1,...,y_{s-1}, L=t)$ (with all $s \ge t+2$) could be identifiable with the help of non-future dependent missing assumption.

For longitudinal data with dropouts, non-future dependent (NFD) missing mechanism (Kenward et al., 2003) assumes that the unidentifiable conditional distributions of y_s ($s \ge t + 2$), given earlier measurements, in Pattern t, is equal to the corresponding distribution in patterns $L \ge s - 1$:

$$f(y_s \mid y_{1,...}, y_{s-1}, L = t) = f(y_s \mid y_{1,...}, y_{s-1}, L \ge s - 1)$$
 (2)

Page 44

The right hand side of (2) can further be partitioned into

$$f(y_s \mid y_l, ..., y_{s-l}, L \ge s-1) = \sum_{j=s-1}^{T} \omega_{s-1, j} \cdot f(y_s \mid y_l, ..., y_{s-1}, L = j)$$
(3)

Where mixture probabilities $\omega_{s-1,j}$ are:

$$\omega_{s-1,j} = \frac{\alpha_j f(y_1, ..., y_{s-1} \mid L = j)}{\sum_{t=s-1}^{T} \alpha_t f(y_1, ..., y_{s-1} \mid L = t)}, \text{ and } \alpha_j \text{ represents the fraction of}$$

$$(4)$$

patients from Pattern *j*.

Each factor of the unidentifiable conditional distribution of y_s ($s \ge t + 2$) on the right side of (1) can be expressed using the following:

- $f(y_s | y_1,...,y_{s-1}, L = s-1)$, the unidentifiable conditional distribution of the first missing in pattern s-1,
- $f(y_s | y_1,...,y_{s-1}, L = j)$, the identifiable conditional distributions of y_s given $y_1,...,y_{s-1}$ of pattern j ($j \ge s$), and
- α_i , the fraction of patients from pattern j ($j \ge s 1$).

So under NFD, all the unidentifiable conditional distribution on the right side of (1) can be estimated and missing value could be therefore imputed based on the assumption for unidentifiable conditional distribution of the first missing.

We re-formulate the partition in (3), for $s \ge t + 2$, as the following:

$$f(y_s \mid y_{I},..., y_{s-1}, L = t) = \delta_{s-1} f(y_s \mid y_{I},..., y_{s-1}, L = s - 1) + (I - \delta_{s-1}) f(y_s \mid y_{I},..., y_{s-1}, L \ge s)$$
(5)

for $s \ge t + 2$ with $\delta_{s-1} = \omega_{s-1,s-1}$.

Therefore, under monotone missing and NFD assumption, the unidentifiable conditional densities for Visit s in Pattern t ($s \ge t + 2$) can be expressed as a mixture distribution of $f(y_s \mid y_1,...,y_{s-1}, L = s - 1)$ - the unidentifiable conditional distribution of the first missing measurement y_s in Pattern s - 1, and $f(y_s \mid y_1,...,y_{s-1}, L \ge s)$ - the identifiable conditional distribution of y_s from all the patterns with observed data at Visit s or beyond:

$$f(y_s \mid y_l, ..., y_{s-l}, L \ge s) = \sum_{j=s}^{T} \lambda_{s-l,j} f(y_s \mid y_l, ..., y_{s-l}, L = j)$$
 (6)

where the mixture probability

$$\lambda_{s-l,j} = \omega_{s-l,j} / (1 - \omega_{s-l, s-l}) = \frac{\alpha_j f(y_l, ..., y_{s-l} \mid L = j)}{T} \quad \text{for } j \ge s, \text{ where } \alpha_j \text{ is the fraction of}$$

$$\sum_{t=s}^{T} \alpha_t f(y_l, ..., y_{s-l} \mid L = t)$$
(7)

patients from Pattern *j*.

The conditional densities for the first missing are selected as:

$$f(y_s | y_{l,...}, y_{s-1}, L = s - 1) = f(y_s - \Delta | y_{l,...}, y_{s-1}, L \ge s)$$
 for $s = 2, ..., T$, (8)

Note that the two distributions only differ by a shift (Δ) parameter. When $\Delta = 0$, the missing value y_s in Pattern s-I is imputed based on the distribution of all observed data up to Visit s, as a result, leading to missing at random (MAR) missingness. When $\Delta \neq 0$, (8) will introduce a scenario of MNAR. The similar idea was also presented in the recent publication "The Prevention and Treatment of Missing Data in Clinical Trials" by the National Academies Press. The selection of the plausible values for the shift parameter (Δ) is discussed in Section 3.0.

Note that per recommendation in Wang and Daniels (2011), only the observed data within pattern is assumed to be multivariate normal. The observed data distribution can be expressed in terms of the marginal distribution of baseline measurement and the conditional distributions of postbaseline measurements given earlier measurements. Assuming that these distributions are normal, the linear regression of each observation on prior observations will yield least-squares estimates of model parameters that can be utilized for independent posterior draws of model parameters for observed data. Multiple imputation approach will be used to estimate the overall mean at the final time point.

2. Imputation Procedure

All the missing data will be imputed to create complete datasets, then statistical analysis can be performed using appropriate techniques such as ANCOVA. The imputation can accommodate MNAR missing data mechanisms, based on the theory discussed in the previous section.

The model parameters for each dropout pattern, i.e., the mean, variance and proportions of observations in each pattern, are drawn from their posterior distributions prior to the imputation of missing data for a single imputation.

The details of imputation within a pattern, say Pattern *t*, are as the following:

Step 1. Impute the first missing value y_{t+1} for each patient in Pattern t (t = 1,..., T-1):

- a. Compute estimates of mixture probabilities $\lambda_{s-l,j}$ in (7) with s = t+1 given the posterior draw of proportions of observations in each pattern and the posterior draw of regression parameters for the observed data.
- b. Draw a random integer from $\{s,...,T\}$ to index a component distribution on the right hand side of (6), using mixture probabilities obtained in a). Draw y_{t+1}^* from the identified component normal distribution. Impute the missing y_{t+1} as $\widetilde{y}_{t+1} = y_{t+1}^* + \Delta$.

Step 2. Impute the rest of the missing values of $y_{t+2}, y_{t+3}, ..., y_T$ for patients in Pattern t:

Starting with imputation for y_{t+2} , first, similar to Step 1, draw y_{t+2}^* from the normal mixture (6) based on the observed $y_l,...,y_t$ and the already imputed \widetilde{y}_{t+1} for the patient. Then the missing y_{t+2} is imputed as $\widetilde{y}_{t+2} = y_{t+2}^* + \Delta$ with probability δ_{t+1} and as $\widetilde{y}_{t+2} = y_{t+2}^*$ with probability $I - \delta_{t+1}$, where the mixture probability $\delta_{t+1} = \omega_{t+1,t+1}$ is obtained from (4) given the posterior draw of proportions of observations in each pattern and the posterior draw of regression parameters for the observed data.

Missing values of y_{t+3} through y_T can be imputed similarly as y_{t+2} .

To summarize, the imputations of y_{t+1} through y_T is done recursively within each Pattern t (for all t = 1,...,T-1) to create a complete dataset after imputation is done for all patterns with missing values.

The above imputation procedure is applied to all subjects in each missing data pattern to create a single imputed data set. Repeating the process of drawing parameters from the posterior distribution and imputing missing data given the posterior draw m times will yield m imputed data sets. The observed or imputed values at the final data point are averaged to obtain the overall mean estimate for each imputed data set, and the multiple imputation estimate is obtained by averaging the estimates across m imputations.

In this sensitivity analysis, m is set to equal to 20. The value of m is discussed in the context of imputation efficiency in standard multiple imputation theory (Rubin, 1987, p. 114), and m = 20 would provide at least 96% of relative efficiency as compared with using a large number of imputations (SAS/STAT User's Guide, p. 3796).

3. Determination of the Shift Parameter Values

The common shift parameter Δ is the difference between the mean of y_{t+1} among those who drop out at Visit t and those who remain beyond Visit t ($1 \le t \le T - 1$). The exact value of Δ is unknown and can't be estimated from data because of missingness. The magnitude of Δ depends on the medical aspects of the trial. Using relevant historical data, one may select Δ as a proportion of the sample standard deviation or a proportion of observed treatment efficacy.

References:

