9.2 MEASUREMENT OF TREATMENT COMPLIANCE

Dosing compliance for a specified period is defined as the number of capsules actually taken by a patient during that period divided by the number of capsules prescribed for the same period multiplied by 100. The total number of capsules actually taken during a specific time period will be calculated from the study medication records. The number of capsules expected to be taken for a specific treatment period will be calculated by multiplying the number of days in that period by the number of capsules prescribed to be taken per day.

Descriptive statistics for investigational product compliance during the double-blind treatment period will be presented by treatment group for each period between 2 consecutive visits, as well as for the whole double-blind treatment period, for the Safety Population.

10.0 EFFICACY ANALYSES

The efficacy analyses will be based on the ITT Population. *Baseline* for efficacy is defined as the last non-missing efficacy assessment recorded at or prior to first dose of investigational product. All statistical tests will be 2-sided hypothesis tests performed at the 5% level of significance for main effects. All confidence intervals will be 2-sided 95% confidence intervals, unless stated otherwise.

For efficacy analyses in which study center is a factor, a small center will be defined as a center with fewer than 2 patients in any treatment group in the ITT Population. Small centers will be pooled to form pseudo-centers so that each treatment group includes at least 2 ITT patients within the center. Pooling will be done using the following algorithm:

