10.1 PRIMARY EFFICACY PARAMETER(S)

The primary efficacy parameter will be the change from baseline in CDRS-R total score at Week 8. The primary analysis for comparing levomilnacipran vs. placebo for the primary efficacy parameter will be performed using an MMRM with treatment group,

pooled study center, visit, and treatment group-by-visit interaction as fixed effects and the baseline value and baseline value-by-visit interaction as covariates. An unstructured covariance matrix will be used to model the covariance of within-patient scores. The Kenward-Roger approximation (Kenward and Roger, 1997) will be used to estimate denominator degrees of freedom. This analysis will only use the observed cases of postbaseline scores without imputation of missing values. In the event of non-convergence of the model using unstructured covariance matrix, a structured covariance matrix will be used in combination with empirical variance estimate (i.e. sandwich estimator) to address the potential mis-specified situation. The following sequence of alternative covariance structures (First-order antedependence [ANTE (1)], Toeplitz [TOEP], First-order autoregressive [AR(1)] and compound symmetry[CS]) will be considered in the MMRM until convergence.

To control the overall type I error rate for the multiple comparisons across the primary and the secondary hypotheses, a fixed sequence procedure will be applied. Details are provided in Section 10.2.

In addition, two sensitivity analyses, LOCF and pattern-mixture model approaches, will be performed on the primary efficacy parameter.

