The LOCF approach is based on an analysis-of-covariance (ANCOVA) model including treatment group and pooled study center as factors and baseline CDRS-R total score as a covariate. The pattern-mixture model approach is based on the non-future dependent missing value restrictions (Kenward et al., 2003) and is performed to assess the robustness of the primary MMRM results to the possible violation of the missing-atrandom assumption. The pattern for the pattern-mixture model will be defined by the patient's last visit with an observed value. The observed CSRS-R total score at a visit is assumed to have a linear relationship with the patient's prior measurements. The missing values will be imputed under the assumption that the distribution of the missing observations differs from that of the observed only by a shift parameter value Δ . The dataset with all missing values imputed will be analyzed using an ANCOVA model with treatment group and pooled study center as factors and baseline CDRS-R total score as a covariate for between-treatment group comparisons at Week 8. The imputation of missing values and the analysis will be performed multiple times and the inference of this sensitivity analysis will be based on the combined estimates using the standard multiple imputation technique. The range of values for the shift parameter Δ is selected as 0 to 6 based on experience with historical data. Technical details of the proposed patternmixture model approach (e.g., the models for the pattern-specific identifiable densities and the unidentified conditional distributions, the shift parameter Δ , and the multiple imputation algorithm) are provided in Appendix I to this SAP.

Graphical display of treatment difference vs. placebo (mean difference \pm SE) in primary efficacy parameter will be provided by pooled study center to examine the consistency of the primary efficacy results across study centers.

The site 0070 ceased operations on October 31, 2020, due to the damage caused by Hurricanes Laura and Delta, which made landfall on August 27, 2020 and October 10, 2020, respectively. One more sensitivity analysis excluding all data from this site will be performed on the primary efficacy parameter. The same MMRM would be applied on all OC of change from baseline to Week 8 in CDRS-R total score except all values of Site 0070.

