The effect size (treatment group difference relative to pooled SD) of 0.36 for both levomilnacipran and fluoxetine is based on a treatment difference of 4 units with a common pooled SD of 11.1 for the primary efficacy parameter, change from baseline to Week 8 in CDRS-R total score. A sample size of 480 patients (160 per treatment group) will be needed to provide 85% power for primary analysis (levomilnacipran vs. placebo) based on an MMRM model using simulation method (Lu, 2012). The simulation assumed a correlation of 0.7 between the repeated measures and a dropout rate of 17% based on historical data in pediatric patients.

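### The pattern-mixture analysis uses one shift Δ for all arms, so at similar dropout it barely moves the treatment difference and tests the primary result only weakly

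*SAP*

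**What the plan says.** SAP Section 10.1 states that "two sensitivity analyses, LOCF and pattern-mixture model approaches, will be performed on the primary efficacy parameter". The same section later adds a run excluding Site 0070. The pattern-mixture model is the one aimed at the missing-data assumption: it is "performed to assess the robustness of the primary MMRM results to the possible violation" of missing at random. Patterns are defined only by the last visit with an observed value. The assumption is that "the distribution of the missing observations differs from that of the observed only by a shift parameter value" Δ, and "The range of values for the shift parameter Δ is selected as 0 to 6 based on experience with historical data".

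In Appendix I, equations (1) to (8) condition on earlier measurements and dropout pattern, never on treatment. Part 3 begins "The common shift parameter Δ is the difference between the mean of" the next value in those who drop out and those who stay. Part 2 closes with "The above imputation procedure is applied to all subjects in each missing data pattern to create a single imputed data set". Protocol Section 9.7.5.1 gives the same single range.

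On dropout, SAP Section 14.0 says: "The simulation assumed a correlation of 0.7 between the repeated measures and a dropout rate of 17% based on historical data in pediatric patients". No rate is given by arm. Neither document plans an arm-specific Δ, a reference-based imputation or a tipping-point search.

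**The concern.** Higher CDRS-R scores are worse, so a positive Δ makes dropouts look worse than missing at random predicts. If it is added to dropouts in both arms, both Week 8 means worsen by similar amounts and the difference stays put. A flat result over Δ = 0 to 6 could then be read as robustness when it follows from the design. The scenario that would threaten a positive trial, in which levomilnacipran dropouts alone do worse than predicted, is never examined. If placebo loses more patients, the intended stress moves the estimate towards the drug.

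A second gap is that Appendix I does not say whether imputation models are fitted within arm or pooled over arms. That choice alone can move the Δ = 0 estimate.

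**Working it through.** Differences are shown as benefit, so positive favours levomilnacipran.

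**Inputs.** From SAP Section 14.0: difference 4, SD 11.1, 160 per arm, correlation 0.7, dropout 17%, power 85%. From Section 10.0: "All statistical tests will be 2-sided hypothesis tests performed at the 5% level of significance for main effects". From Section 4.0: six postbaseline visits. From Section 10.1: Δ from 0 to 6. The splits 22%/12% and 12%/22% (levomilnacipran/placebo) are assumptions, because the documents give no rates by arm.

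**1. The plan's power.** With completers only, n = 160 × 0.83 ≈ 133 per arm and SE = 11.1 × √(2/133) = 1.36. Power is Φ(4/1.36 − 1.96) = 83.6%. An MMRM information calculation (compound symmetry, dropout spread evenly) gives SE 1.29 and 87.2%. The stated 85% lies between, so the inputs are coherent.

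**2. Closed form, full shift kept to Week 8.** With dropout fractions d_L and d_P:
- common Δ: difference = 4 − Δ(d_L − d_P)
- levomilnacipran-only Δ: difference = 4 − Δ·d_L

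At 17%/17% and Δ = 6, the common shift gives 4 − 6 × 0 = 4.00. The levomilnacipran-only shift gives 4 − 6 × 0.17 = 2.98.

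**3. Appendix I propagation.** Only the first missing value always receives Δ. Later ones receive it with probability δ, which is small: if 0.17/5 = 0.034 of patients leave after each of five visits, δ is about 0.04. The rest is carried through regression on earlier values. In simulation, the mean Week 8 shift among dropouts at Δ = 6 is 2.46. The expected fall for a levomilnacipran-only shift is therefore 0.17 × 2.46 = 0.42.

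**4. Large-sample simulation, imputation within arm.** Run A (150,000 per arm) uses the full Appendix I mixture. Dropout depends on the last observed score, and the effect grows from 0.5 to 4.0 over visits (both assumed). Run B (400,000 per arm) takes dropout unrelated to outcome.

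| Dropout L/P | Run | Δ = 0 | Common Δ = 6 | Levomilnacipran-only Δ = 6 |
|---|---|---|---|---|
| 17%/17% | A | 3.97 | 3.98 | 3.50 |
| 17%/17% | B | 3.99 | 3.99 | 3.56 |
| 22%/12% | A | 4.00 | 3.71 | 3.38 |
| 22%/12% | B | 4.02 | 3.76 | 3.46 |
| 12%/22% | A | 4.01 | 4.33 | 3.69 |
| 12%/22% | B | 4.06 | 4.31 | 3.76 |

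**5. A borderline result (assumed).** Take an observed difference of 2.8 with SE 1.29 and 17% dropout in each arm: z = 2.17, p about 0.03. Common Δ = 6 leaves 2.8. Levomilnacipran-only Δ = 6 gives 2.8 − 0.42 = 2.38, z = 1.84, p about 0.07. With the full shift at Week 8 it gives 2.8 − 1.02 = 1.78, z = 1.38, p about 0.17.

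**6. Trial level.** 1,500 trials per scenario, 160 per arm, 20 imputations, Rubin's rules. Arm-by-pattern cells hold about five patients (0.17 × 160 ≈ 27, over five patterns), so this run used one within-arm regression per visit and approximated δ by pattern fractions. At Δ = 0 and 17%/17% it gives SE 1.30 and 87% significant. The table shows the share of significant trials that lose significance at Δ = 6:

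| Dropout L/P | Common | Levomilnacipran-only |
|---|---|---|
| 17%/17% | 2.1% | 11.4% |
| 22%/12% | 8.6% | 15.5% |
| 12%/22% | 0.2% | 7.5% |
| 17%/17%, p from 0.01 to 0.05 | 9.9% | 54.6% |

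At the planned effect, the average levomilnacipran-only tipping point lies between Δ = 15 (2.88/1.36, z = 2.12) and Δ = 18 (2.65/1.38, z = 1.92).

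**7. Within arm or pooled.** Pooling the two arms with no treatment term gives 3.43 (run A) or 3.46 (run B) at Δ = 0, against 3.97 and 3.99 within arm. In run B the pooled estimate still does not respond to a common Δ (3.44 to 3.47 over 0 to 6).

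**The case against.** **LOCF already pushes against the drug.** At 17%/17%, under the same growing effect, LOCF gives about 3.6 to 3.7, most of the fall that a levomilnacipran-only Δ of 6 produces. At 22%/12% it gives roughly 2.5 to 2.9, which is harsher. The figures are right, but LOCF is one fixed assumption. At 12%/22% it swings to about 4.3 to 4.7, in the drug's favour. (The unequal-dropout figures depend on an assumed placebo improvement.) It has no parameter that can be raised to find where the result fails.

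**At the planned effect little changes.** This stands. The average tipping point of 15 to 18 is 2.5 to 3 times the top of the planned range and above the SD of 11.1. Trials with p from 0.01 to 0.05 are about 18% of all trials at effect 4 and SE 1.30. The concern is about borderline results, which is where a sensitivity analysis is most needed.

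**The trial-level percentages do not come from the exact Appendix I procedure.** True, and they should be read as approximate. The large-sample differences in run A do follow it, and the cancellation does not depend on the approximation.

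**The wording may mean something narrower.** Part 3 of Appendix I defines Δ over dropout visits, so common may mean common across visits, and the notation is written for a single sample. That is a fair reading, but nothing elsewhere in either document lets Δ differ by arm.

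**The 17% is a sample-size input, not a forecast by arm.** Also fair. With unequal dropout a common Δ of 6 moves the estimate by about 0.3, in a direction set by which arm loses more patients.

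**The question of pooling is separate.** It is, and the 3.43 adds nothing to the argument about Δ.

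**Conclusion.** The concern holds. As written, the only planned analysis with a variable departure from missing at random uses one Δ for all arms. At equal 17% dropout, Δ = 6 changes the difference by 0.01 or less, against a fall of 0.43 to 0.47 when only levomilnacipran dropouts are shifted (1.02 if the full shift persists to Week 8). With more placebo dropout, the common shift helps the drug.

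The size rests on the plan's effect, SD, correlation and overall dropout, and on assumed dropout mechanisms and arm splits. The cancellation itself needs only similar dropout in amount and timing. The primary MMRM is unaffected. What is weakened is the claim of robustness that a flat Δ profile would appear to support. The plan should be changed, but the point does not threaten the trial's validity.

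**What to change.** In SAP Section 10.1 and Appendix I:

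- Keep the common-Δ analysis.
- Add a run with Δ applied only to levomilnacipran dropouts and placebo Δ = 0, stepped over 0 to 6 and onward until the two-sided p-value exceeds 0.05.
- Report that tipping point and judge its plausibility against the historical data behind the 0 to 6 range.
- State that imputation models are fitted within treatment arm.
- State the fallback for patterns too small to fit, for example one regression per visit on all patients of that arm observed there.

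Protocol Section 9.7.5.1 describes the same single-Δ analysis. The new run adds to it, so it can be recorded in SAP Section 18.0, which now lists no changes. This should be settled before unblinding.

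The cost is SAP wording and a few imputation runs, with no new data and no change in conduct. The sensitivity results may look less favourable. Placebo Δ = 0 is itself untestable, which is why the common-Δ run should stay beside it.

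### Twenty imputations are enough for the pattern-mixture estimate, but they leave avoidable seed-to-seed noise in its p-value that matters when the p-value lies near 0.05

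*SAP*

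**What the plan says.** SAP Section 10.1 names the analyses that support the primary MMRM: "two sensitivity analyses, LOCF and pattern-mixture model approaches, will be performed on the primary efficacy parameter". In the pattern-mixture analysis, missing CDRS-R totals are imputed with a shift Δ. On the completed data, "The dataset with all missing values imputed will be analyzed using an ANCOVA model with treatment group and pooled study center as factors", with the baseline score as covariate. The "inference of this sensitivity analysis will be based on the combined estimates using the standard multiple imputation technique". The "shift parameter Δ is selected as 0 to 6 based on experience with historical data".

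Appendix I, part 2 (Imputation Procedure), fixes the number of imputations: "In this sensitivity analysis, m is set to equal to 20". The justification is that "m = 20 would provide at least 96% of relative efficiency as compared with using a large number of imputations".

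The readable text of both documents gives no random seed, no limit on Monte Carlo error in the p-value and no rule for raising m. Section 4.0 says that table, figure and listing specifications are in a separate document, so a seed may be recorded there.

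**The concern.** Relative efficiency says how much the variance of the pooled estimate grows because m is finite. It does not say how far the pooled test statistic moves when the same data are imputed again with another seed. A plan can meet an efficiency target comfortably and still report a p-value that changes visibly from run to run.

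This analysis is run over a range of Δ, and readers will look at how the treatment comparison changes as Δ grows. If each Δ gets its own independent set of 20 imputations, simulation noise is added to that trend. Near 0.05, the side of the line on which a result falls can then depend on the seed.

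**Working it through.** **Inputs.** m = 20 and Δ from 0 to 6 (SAP Appendix I and Section 10.1). 160 patients per arm, a difference of 4 units, SD 11.1, correlation 0.7 and 17% dropout (SAP Section 14.0). Six post-baseline visits at Weeks 1, 2, 3, 4, 6 and 8 (SAP Section 4.0). Two-sided 5% level (SAP Section 10.0). The FMI is not stated, so it is derived here as an assumption.

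**1. The plan's own figure.** Relative efficiency is RE = 1/(1 + FMI/m). With m = 20:

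| FMI | RE |
|---|---|
| 0.08 | 99.6% |
| 0.17 | 99.2% |
| 0.70 | 96.6% |
| 0.83 | 96.0% |

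The stated 96% is correct for any FMI up to 0.83, and this trial should be far below that.

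**2. FMI from the design inputs.** Assume compound symmetry with ρ = 0.7. With k earlier visits observed, the squared multiple correlation with Week 8 is R² = kρ²/(1 + (k − 1)ρ). With dropout d, the variance at Week 8 relative to complete data is v = R² + (1 − R²)/(1 − d), and FMI = 1 − 1/v.
- All dropout after Week 1 (k = 1): R² = 0.49; v = 0.49 + 0.51/0.83 = 1.1045; FMI = 0.095.
- All dropout after Week 6 (k = 5): R² = 2.45/3.8 = 0.645; v = 0.645 + 0.355/0.83 = 1.073; FMI = 0.068.
- Dropout spread evenly over visits: v = 1.083; FMI = 0.076.

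As a check on these inputs, power is 83.6% with 133 completers per arm, and 86.6% to 87.5% from v = 1.1045 and 1.073. These figures bracket the stated 85%.

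**3. Seed-to-seed noise.** The Monte Carlo variance of the pooled estimate is B/m, where B is the between-imputation variance. Since B is FMI times the total variance, SD(z) ≈ √(FMI/m). At m = 20 this is √(0.068/20) = 0.058 to √(0.095/20) = 0.069.

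**4. Range of p when the limiting p is 0.05.** Take z = 1.96 ± 1.96 × SD(z). At FMI 0.08, SD(z) = √0.004 = 0.063, so z runs from 1.836 to 2.084 and p from 0.066 down to 0.037. Over FMI 0.068 to 0.095 the lower limit is 0.036 to 0.038 and the upper 0.065 to 0.068.

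A simulation used 160 per arm, sequential-regression imputation with posterior draws, Rubin pooling with small-sample degrees of freedom, and 3000 sets of 20 per data set. It gave mean FMI 0.083 at Δ = 0 and 0.082 at Δ = 6, with a central 95% range of 0.037 to 0.070 at both. With correlation 0.5 the simulated range was 0.035 to 0.074. With FMI 0.17 (nothing recovered from earlier visits) the formula gives 0.032 to 0.075.

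**5. Effect of m** (FMI 0.08, limiting p 0.05, formula of step 4):

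| m | Central 95% of seeds |
|---|---|
| 20 | 0.037–0.066 |
| 100 | 0.044–0.057 |
| 200 | 0.046–0.055 |
| 500 | 0.047–0.053 |
| 1000 | 0.048–0.052 |

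**6. How often it matters.** At FMI 0.08 and m = 20, a limiting p of 0.045 is reported above 0.05 by about 24% of seeds, and a limiting p of 0.040 by about 7%. At m = 500 the first figure is about 0.02%. With SD(z) = 0.07, a limiting p of 0.03 gives 0.021 to 0.042, and about 0.1% of seeds cross 0.05. Suppose this analysis had the primary's design mean at 85% power, with z normal and unit variance. Two independent seeds would then disagree about 0.05 in about 1.8% of trials; under the null, in about 0.9%.

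**7. Trend over Δ.** The same Δ is applied in every arm, so the arm difference moves roughly by Δ times the between-arm difference in dropout. The documents do not give that difference. The standard error is about 11.1 × √(2/160)/√0.92 = 1.29. Assumed dropout differences of 0, 5 and 10 percentage points then move z by about 0, 0.05/1.29 = 0.04 and 0.10/1.29 = 0.08 per unit of Δ. Two independent runs at m = 20 differ by noise with SD √2 × 0.063 = 0.09. The noise can therefore be as large as the step being read.

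**The case against.** The strongest reply is that nothing decisive rests on this p-value. The primary test is an MMRM on observed cases without imputation (SAP Section 10.1), and the fixed sequence covers only the primary and secondary parameters (Section 10.2). The pattern-mixture analysis is supportive. A reader might infer that robustness is lost once p exceeds 0.05 at some Δ, but the SAP sets no such rule and no tipping-point criterion. All of this stands.

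It is also fair to say that the 0.037 to 0.070 range is the least favorable case, because it fixes the limiting p at exactly 0.05. A reader might take it to mean that the p-value is unstable in general; step 6 shows that it is not. A reader might also infer that the 96% efficiency figure is wrong; step 1 shows that it is right.

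The simulation is not a full copy of Appendix I. It pooled regressions over dropout patterns, approximated the mixing probabilities by pattern fractions and left out pooled center. The order of magnitude is supported, the third decimal is not, and pattern-specific regressions with few dropouts could widen the range. Finally, a seed may be recorded in documents not available here. A seed alone, however, would fix one draw without making it less noisy.

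**Conclusion.** The point holds as a low-cost improvement, not as an error. Twenty imputations are adequate for the estimate, at about 99.6% efficiency. They leave a seed-to-seed SD of about 0.06 to 0.07 in z. If the limiting p is 0.05, the central 95% of seeds give about 0.037 to 0.070, and single runs can fall outside that range. Away from 0.05 the conclusion is rarely affected, and the confirmatory test is untouched.

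The size rests on an FMI of about 0.07 to 0.10, derived from 17% dropout and correlation 0.7 under compound symmetry. More dropout or weaker correlation would widen the range.

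**What to change.** In SAP Appendix I, part 2, raise m to at least 200, for example 500, and base the choice on Monte Carlo error in the p-value as well as on relative efficiency.

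Prespecify one seed and restart it for every Δ, so that all values of Δ share common random numbers. Identical imputed values across Δ are not possible, because Step 2 of the procedure conditions each later value on the one already shifted. The program should use the same number of random draws per missing value whatever Δ is, so that the streams stay aligned.

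The cost is minutes of computing and a sentence or two in the SAP. No endpoint, estimand or confirmatory test changes. Settling it before unblinding also removes any question about how the seed was chosen.
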